Effects of HRVB on Veterans with Chronic Pain. This study⁵⁰ determined the effectiveness of HRV-B as a pain management intervention for DVAMC Veterans with chronic pain by comparing pre- and post-intervention pain and stress scores among two groups of randomly assigned Veterans that met the chronic pain inclusion criterion. One group received HRV-B plus treatment as usual and the other group received only treatment as usual. The outcomes of this study were HRV coherence and four scale scores (pain, emotional distress, activity limitation, and stress) that were obtained from two previously validated psychometric instruments (BPI and PSS, respectively). Veterans receiving HRV-B training were coached to use constructive processes to engage and manage internal sensations of pain rather than rely on strategies of avoidance. All subjects received a baseline and a follow-up assessment after 6 weeks of HRV-B training or treatment as usual. Retention for this pilot study was 100%. The HRV-B group received five weekly HRV-B training sessions. Treatment effects were analyzed with ANCOVA of follow-up scores by group using baseline scores as covariates. Eight Veterans completed the HRV-B intervention and six Veterans in the usual treatment group returned for a follow-up assessment. The mean baseline values for the two groups were not statistically different for any of the measures. In the HRV-B group, there was a statistically significant increase in HRV coherence and a reduction among each of the four outcome measures for pain or stress post-HRV-B training relative to the group that only received usual treatment (all $p < 0.05$, Figure 4). Results from this study indicate that HRV-B can effectively reduce the negative perceptions of pain. Data obtained from this investigation were used to develop statistical power and sample size estimates since they are most directly relevant to the proposed intervention.

Post-treatment coherence ratios were significantly different ($U = 7.0, p_{11} = .03$) but pre-treatment ratios were not (Treatment $n=8$, Control $n=6$).

[figure not shown]

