2.3 Data Analysis Plan

Statistical Power & Sample Size. Preliminary data for HRV coherence and the pain (BPI), and stress (PSS) scales from our HRV-B pilot study among DVAMC chronic pain patients were used to estimate statistical power for the proposed primary study outcomes (HRV coherence, pain rating, negative emotion, activity limitation, perceived stress scale). Two-sided, two sample t-tests were used for the statistical power calculations. The analysis for the proposed study will use more sophisticated methods that tend to reduce variance in the dependent variables and thus increase power, thus what is presented here is likely conservative. An overall significance level of 0.05 was used with correction for multiple testing via the Bonferroni method for the 5 outcomes (adjusted significance level = 0.01; 0.05/5). Our pilot data indicate that at baseline, no statistical differences were observed between treatment groups for any outcome. The detectable effect differences between treatment and sham groups with corresponding standard deviations are presented in Table 3. We assumed equal variances in the differences between pre- and post-treatment comparisons for both groups. A sample size of 25 in each group will attain a statistical power of at least 84.5% to detect the expected effect differences between treatment groups, and groups sizes of 40 patients will provide statistical power exceeding 95% for comparisons between treatment groups for each outcome. Thus, a sample size of 40 patients per group would achieve ample statistical power even with retentions on of 55-60%.

Table 3. Estimated Power for Differences Between HRV-B Treatment & Sham Interventions

Sample Size per Group	Negative Emotion (4.5±10; 15.5±10)*	Activity limitation (4± 9.5; 14± 9.5)*	Pain Rating (1.8±5.0; 10±5.0)*	Perceived Stress (-1.2±4.5; 4±4.5)*	HRV Coherence (-0.03±0.15; -0.20±0.15)*
22	82.3%	78.1%	99.6%	86.5%	84.9%
25	88.1%	84.5%	99.9%	91.4%	90.2%
30	94.1%	91.7%	99.9%	96.2%	95.4%
40	98.7%	97.9%	99.9%	99.3%	99.1%

*Average pre-post change ± SD in the control group; and average pre-post change ± SD in the treatment group, respectively

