For each of the outcomes, there will be three measurements per subject (post-training minus pre-training, 4-week booster minus post-training, and 8-week follow-up minus the 4-week booster assessment). To test the effect of HRV-B relative to controls, we will apply linear mixed models for repeated measures data. Models will include the group (intervention or sham), time, and the interaction between group and time as the main independent variables. The effect of the intervention on the outcome could be non-linear in time, thus we will evaluate the inclusion of time as a nominal or ordinal variable and choose the specification that has the best fit in terms of the model assumptions and the BIC statistic. Covariates to be considered in the models include (but are not limited to: age, type and duration of usual pain treatment or medication, or other outcomes that may modify the effect (e.g., stress, pain, sleep). We will use a variable selection procedure to screen and identify all variables that differ among the treatment and control groups (initial selection set at $p < 0.15$), and we will include them in the final statistical model if their inclusion alters the effect estimate for HRV-B by $\geq 10\%$. Linear mixed effect models will be implemented using the PROC MIXED procedure in SAS (v9.3, SAS Institute). The conceptual model of each linear mixed model is:

$$Y_{ij} = \beta_0 + \beta_1 X_{ij} + \beta_2 t_j + \beta_3 X_{ij} \times t_j + s_i + \varepsilon_{ij},$$

where Y is the dependent variable, X is the independent variable of interest (or a vector of covariates), s_i is a subject-specific random effect, and t represents the outcome assessment time points (baseline, follow-up). The β coefficients measure each independent variable's effect. If time is included as an ordinal variable,

significance between treatment and control groups will be tested using Wald tests for appropriate β coefficients. If time is included as a nominal variable, we will use least squared means to test for significant differences between treatment and control groups at each of the post-intervention time points (post-training, booster, 8-week follow-up). In this situation we will use a Bonferroni adjusted alpha level = 0.005 (0.05/10), which results in at least 78% power for all of the outcomes with 25 per group to account for attrition (data not shown).

[figure not shown]

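### The covariate rule drops prognostic covariates that randomisation happens to balance, and no outcome's own baseline score is a fixed model term

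*Combined protocol and SAP*

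**What the plan says.** Section 2.3 (Statistical Analyses) puts group, time and group-by-time in every linear mixed model. The list of other candidates is open. Step 1 is to "screen and identify all variables that differ among the treatment and control groups", with entry at p<0.15. Step 2 is a change-in-estimate test: "we will include them in the final statistical model if their inclusion alters the effect estimate for HRV-B by" 10% or more. The outcome's own T-1 score is neither a fixed term nor a named candidate.

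Three other places bear on this:

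- **Pilot (Section 1.1).** The study that supplied the power inputs did adjust for baseline: "Treatment effects were analyzed with ANCOVA of follow-up scores by group using baseline scores as covariates".
- **Covariates promised elsewhere.** Section 2.1 commits two pain-duration variables to the analysis with no screen. The Section 2.0 overview gives a further set of examples: age, standard therapy, medications and co-morbidity.
- **Response.** Section 2.3 says "there will be three measurements per subject (post-training minus pre-training, 4-week booster minus post-training, and 8-week follow-up minus the 4-week booster assessment"), which are successive changes. Its model equation then says "t represents the outcome assessment time points (baseline, follow-up"), which suggests raw scores with baseline as a time level.

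On power, the same section says the analysis "will use more sophisticated methods that tend to reduce variance in the dependent variables and thus increase power", and that "a sample size of 40 patients per group would achieve ample statistical power even with retentions on of 55-60" per cent.

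**The concern.** Allocation is randomised, so any between-arm difference in a baseline variable is chance. A screen on that difference selects for imbalance, whereas precision comes from prognostic strength. A variable that strongly predicts the outcome but is balanced fails step 1 and never reaches step 2.

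Two things are at stake. The first is precision: the pre-training score, usually an obvious candidate for adjustment, would be left out most of the time. The second is pre-specification: nobody can say in advance which covariates the main model for a given outcome will contain, because step 2 depends on the estimated treatment effect. The unscreened commitment in Section 2.1 also conflicts with the conditional rule in Section 2.3.

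**Working it through.** **1. The plan's own power figures.** Activity limitation is the weakest outcome in Table 3: mean changes 4 and 14, SD 9.5, so d = 10/9.5 = 1.053. A noncentral-t calculation for a two-sided two-sample t-test at alpha 0.01 gives 78.1%, 84.5% and 97.9% at 22, 25 and 40 per arm, matching the table. At alpha 0.005 (the branch with time as nominal) it gives 69.8%, 77.7% and 96.3%. The middle value agrees with the plan's statement, "which results in at least 78% power for all of the outcomes with 25 per group to account for attrition". These figures use SDs of change and no covariate.

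**2. Step 1.** A baseline variable unrelated to allocation has p<0.15 with probability 0.15, so it is excluded with probability 0.85. If the screens for the five outcomes' own baselines were independent (an assumption), none would pass with probability 0.85^5 = 0.44 and all five with 0.15^5 = 0.00008. In about 56% of trials some outcomes would pass and others would not.

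**3. Step 2.** The shift in the estimate is the within-arm slope of outcome on covariate times the arm difference in the covariate, so this step does respond to prognosis. In simulation (40 per arm, d=1.05, 40,000 trials), among covariates passing step 1 it kept about 5% at within-arm correlation 0, 62% at 0.3, 96% at 0.5 and nearly all at 0.7. The loss therefore occurs at step 1.

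**4. Fixing baseline, pre-post change contrast.** Let ρ be the pre-post correlation and k the post/pre SD ratio. Neither is in the documents. The large-sample variance ratio, adjusted to unadjusted, is

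k²(1−ρ²) / (1 + k² − 2ρk).

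- k=1: (1+ρ)/2 = 0.65, 0.75, 0.85, 0.90 at ρ = 0.3, 0.5, 0.7, 0.8.
- k=1.23: 0.776, 0.885, 0.976, 1.000. The gain is zero when ρk = 1.

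The value 1.23 is illustrative. It comes from the CAPS table in Section 1.1 (SE×√n, pooled over arms: 22.3 pre, 27.5 post), which is a different outcome in a PTSD sample.

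**5. Simulated power**, activity limitation, 25 per arm, alpha 0.005, baseline as the candidate, 40,000 trials per setting (Monte Carlo SE at most about 0.2 points):

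| ρ | Unadjusted | Rule, k=1 | Fixed, k=1 | Rule, k=1.23 | Fixed, k=1.23 |
|---|---|---|---|---|---|
| 0.3 | 78% | 81% | 94% | 80% | 88% |
| 0.5 | 78% | 80% | 90% | 79% | 83% |
| 0.7 | 78% | 79% | 85% | 78% | 78% |
| 0.8 | 78% | 79% | 82% | 78% | 76% |

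At k=1 the rule admitted baseline in only 11% to 15% of these trials.

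**6. Interval width at 40 per arm**, fixed baseline relative to the rule: 0.833, 0.886, 0.935, 0.959 at k=1, and 0.900, 0.951, 0.995, 1.006 at k=1.23. At 25 per arm with k=1.23 and ρ=0.8 the ratio is about 1.01.

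**7. Type I error.** With baseline as the only candidate and no true effect, the rule rejected between about 3% and 5% of the time at nominal 5%.

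**8. If raw scores are modelled with baseline as a time level.** The equation in Section 2.3 has a random intercept and one residual variance, so it pools variance over visits. With complete data at four visits, the ratio of interval widths at a visit is √{k²(1−ρ²) / [(1+3k²)/4]}. Narrowing is 5/13/29/40% at k=1 and 0.3/10/25/37% at k=1.23. At k=2.77 it is 8% wider, then 2/19/32% narrower. (2.77 is the RMSSD ratio 63.2/22.8 from Section 1.1, one arm at one visit, reading the bracketed values as SDs.) The benefit depends on k here too.

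**The case against.** The case for leaving the plan alone has real substance.

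- **Power is already high.** With 40 per arm retained it is at least 97.9% at alpha 0.01, and the pilot reported full retention. This stands. The 22 to 25 per arm case is a contingency, though one the plan itself provides for.
- **Baseline is already used by subtraction** if successive changes are the response. This stands too: the gap is change score against baseline adjustment, and it can be nil.
- **The later successive differences gain little.** Under compound symmetry they gain nothing, and under AR(1) at most about 7% of variance.

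A reader might infer more than the documents support:

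- *That the power section depends on covariate adjustment and is therefore wrong.* It does not. The remark about variance reduction is general and unquantified, no printed figure uses it, and Table 3 reproduces without it.
- *That the rule ignores prognosis altogether.* Step 2 responds to it strongly; the fault is that step 1 comes first.
- *That the rule inflates type I error.* With baseline as candidate it did not. The full open list, which includes other outcomes, was not tested, so nothing is claimed there either way.

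**Conclusion.** The point holds as a worthwhile improvement in efficiency and pre-specification, not as a validity failure. A balanced prognostic covariate is lost about 85% of the time, and the model for each outcome is not settled in advance. The conflict between Sections 2.1 and 2.3 over the pain-duration covariates is plain on the text and does not depend on any assumption.

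The precision gain does depend on assumptions. At 25 per arm and alpha 0.005, fixing baseline rather than applying the rule adds about 13 points of power at ρ=0.3 and k=1, and costs up to about 2 points at ρ=0.8 and k=1.23. At 40 per arm, intervals are 17% to 4% narrower at k=1, and range from 10% narrower to 0.6% wider at k=1.23. Confidence in the size is moderate because ρ and k for the trial's own outcomes are not given.

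**What to change.** In Section 2.3, Statistical Analyses:

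1. State which response is modelled. For post-training responses, include the outcome's T-1 score and its interaction with visit as fixed terms in every main model. If baseline is kept as a response, constrain the two arms to a common baseline mean.
2. Pre-specify one short covariate list for all main models. Carry in the two pain-duration variables from Section 2.1, and settle which of the Section 2.0 examples are fixed.
3. Move the p<0.15 screen and the 10% change-in-estimate rule to a labelled sensitivity analysis.

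The cost is SAP wording and about one degree of freedom per term. No new data are needed. In the least favourable case examined, intervals widen by about 1%.

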2.0 STUDY DESIGN AND METHODS

Overview. The proposed intervention will use a previously approved, standardized HRV-B training protocol.⁴⁴ The primary (HRV coherence, pain, stress) and exploratory outcomes (insomnia, fatigue, depression, cognition) will be assessed at baseline, after the 6 weekly treatments, at the 4-week post-training booster, and at the 8-week post-training follow-up. Standardized procedures will characterize HRV coherence and other frequency- or time-domain HRV measures, and validated instruments will be used to assess pain^{64,65} and

stress.⁶⁶ Sham intervention subjects will have pulse and respiration monitored but not receive active training; instead they will view a static, relaxing nature picture on a computer screen. We will provide portable data-logging devices for practicing HRV-B at home, and sham devices. Wrist actigraphy will characterize insomnia via continuous, 24-hour/day personal monitoring of rest/activity rhythms at 1-week intervals coinciding with the baseline, post-training, and 8-week follow-up assessments only.^{58,67-69}

Data analyses will test for differences in primary and secondary endpoints at baseline, after 6 weeks of active versus sham HRV-B treatment, at the 4-week post-training booster/assessment, and 8 weeks after training. Analyses will be based on intent to treat with two-sided tests. The effect of HRV-B on coherence and other HRV variables will be analyzed using linear mixed models for repeated measures data from sequential time assessments, and a between-subjects factor to evaluate the intervention after adjusting for potential confounding factors (e.g., age, standard therapy, medications, co-morbid disease). Baseline relationships between HRV coherence and endpoints will be examined using multiple regression models. Few studies have examined the multivariate relationship between pain, autonomic dysfunction, stress, depression, sleep, rest/activity rhythms, fatigue, and cognition. Path analyses will be used to model interrelationships between HRV-B, primary and exploratory outcomes, and behavioral or social factors that facilitate the persistence of HRV coherence and pain management effectiveness.

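### If the main model is fitted to the three adjacent changes with only a random intercept, the averaged HRV-B effect is tested with too large a standard error, and the booster and 8-week tests cannot show sustained benefit

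*Combined protocol and SAP*

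**What the plan says.** Section 2.3, Statistical Analyses, states that for each outcome "there will be three measurements per subject (post-training minus pre-training, 4-week booster minus post-training, and 8-week follow-up minus the 4-week booster assessment". The summary that opens the document describes the same three change estimates.

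On the model, section 2.3 says: "Models will include the group (intervention or sham), time, and the interaction between group and time as the main independent variables". Its equation has these terms, a residual, and one term for dependence within a patient: "s_i is a subject-specific random effect". The model is to be "implemented using the PROC MIXED procedure in SAS". No other covariance structure, unbounded variance or robust standard error is mentioned. BIC is used only to choose between nominal and ordinal time.

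Two routes to inference are named:

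- Ordinal time: "significance between treatment and control groups will be tested using Wald tests for appropriate" coefficients.
- Nominal time: "we will use least squared means to test for significant differences between treatment and control groups at each of the post-intervention time points", at alpha 0.005.

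The Overview in section 2.0 refers to "a between-subjects factor to evaluate the intervention" but names no particular contrast. Section 2.3 also defines the time index as including baseline, and a change score has no baseline row.

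**The concern.** Write T1 to T4 for the four assessments and D1 = T2-T1, D2 = T3-T2, D3 = T4-T3. T2 enters D1 with a plus and D2 with a minus, and T3 does the same for D2 and D3. Measurement noise at a visit therefore pushes two neighbouring changes in opposite directions. A random intercept implies one common correlation that is zero or positive. Faced with negative correlation, its variance is estimated at or near zero and the three changes are treated as independent.

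Two things are at stake. First, the sum D1+D2+D3 equals T4-T1, so the averaged group effect is one third of the 8-week benefit since baseline. That contrast speaks to persistence, and it is the one whose standard error is wrong. Second, single-time comparisons of adjacent changes answer a different question after post-training. If a benefit gained by T2 is fully kept, the expected group differences in D2 and D3 are zero.

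**Working it through.** **Inputs from section 2.3 and Table 3.** Smallest standardised effect: activity limitation, change 14 versus 4, SD 9.5, so 10/9.5 = 1.05. Two-sided alpha is 0.01. Group sizes are 40 (planned) and 25 (attrition case). Variances of change are assumed equal between arms.

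**Assumed, because the documents do not give it.** The correlation of the four visit scores: either exchangeable, or AR(1) with correlation rho. The treatment effect is taken to appear by post-training and to persist.

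**1. The plan's own figures.** Exact noncentral-t power for activity limitation at alpha 0.01 is 78.1, 84.5, 91.7 and 97.9% for 22, 25, 30 and 40 per group, as in Table 3. At alpha 0.005 with 25 per group it is 77.7%, against the stated 78%.

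**2. Correlation of the changes.** With exchangeable scores, the covariance of (D1, D2, D3) is proportional to [[2,-1,0], [-1,2,-1], [0,-1,2]], so adjacent changes correlate -0.5 and the outer pair 0. With AR(1), adjacent changes correlate -(1-rho)/2. In simulated balanced fits with the intercept variance bounded at zero, that variance was estimated as zero in 100% of exchangeable trials, 96-100% for AR(1) 0.5-0.7 and 73-79% for AR(1) 0.9.

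**3. Standard error of the averaged change.** True variance is Var(T4-T1)/9, while the model uses Var(D)/3.

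- Exchangeable: (2/9)/(2/3) = 1/3, so the model SE is √3 = 1.73 times the truth.
- AR(1): the ratio is (1 + rho + rho²)/3, which is 0.58, 0.73 and 0.90 at rho 0.5, 0.7 and 0.9. The model SE is 1.31, 1.17 and 1.05 times the truth.
- Random walk: adjacent changes are uncorrelated and nothing is lost.

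**4. Power of the averaged group test, activity limitation, 40 per arm.** The estimate is 10/3 = 3.33. The model SE is √(2/40) × 9.5/√3 = 1.226, so the expected statistic is 2.72, against a critical value of 2.64 (78 df). With exchangeable scores the statistic's SD is 1/√3 = 0.577, and power is Φ((2.72-2.64)/0.577), about 55%. With AR(1) 0.7 its SD is √0.73 = 0.854 and power is about 54%. Simulation agrees:

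| Setting (alpha 0.01) | Random intercept | Correct SE |
|---|---|---|
| Activity limitation, exchangeable, 40 per arm | 56% | 98% |
| Activity limitation, exchangeable, 25 per arm | 20% | 84% |
| Activity limitation, AR(1) 0.7, 40 per arm | 54% | 71% |
| Activity limitation, AR(1) 0.7, 25 per arm | 26% | 44% |
| Stress, exchangeable, 40 per arm | 71% | 99% |
| Pain, exchangeable, 40 per arm | 99.5% | 100% |
| Pain, exchangeable, 25 per arm | 87% | 99.8% |

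With no effect, the averaged test rejects in about 0.1% of exchangeable trials at nominal 5%.

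**5. Group-by-time, two degrees of freedom.** The contrast D2-D1 has true variance 2+2+2 = 6 but model variance 4, so its SE is √(4/6) = 0.82 of the truth. Simulated null rejection is about 10% at nominal 5% (exchangeable), 6.5-9% for AR(1) 0.5-0.7 and about 6% for AR(1) 0.9. At nominal 1% it is about 3.3% (exchangeable).

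**6. The tests the plan names.**

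- Single-time LS means: 4.5-5.8% at nominal 5%.
- Ordinal-time slope: 4.6-6.7%. It rests mainly on D3-D1, whose true variance of 4 the model gets right under exchangeability.
- Ordinal-time group coefficient: 2.2-6.0%, depending on how time is coded and on the correlation.
- Post-training comparison, activity limitation, 40 per arm: about 98%, against 97.9% in Table 3.
- Booster and 8-week LS means with a fully sustained effect, 40 per arm, AR(1) 0.3-0.9: 0.8-1.2% rejection at alpha 0.01, which is no power beyond the type I rate.

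**The case against.** The strongest reply is that the two tests that misbehave are not the ones section 2.3 names. Its nominal-time route uses LS means at single time points, and its ordinal-time route uses Wald tests on coefficients. Both stay near their level. No averaged group test is specified; the Overview's mention of a between-subjects factor says only that group is in the model. This stands, and it limits the point.

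A reader might infer that the trial's overall test of HRV-B loses most of its power and that its group-by-time test is invalid. The documents do not support that. A loss of most of the power occurs only at about 25 per arm, for outcomes other than pain, with exchangeable or nearly exchangeable scores. Over-rejection beyond the modest ordinal-slope excess concerns the two-degree-of-freedom interaction under nominal time, where the plan uses LS means instead.

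It can also be said that the outcome may be the visit score. The equation is labelled conceptual, time is said to include baseline, and the named time points are visits. If so, the negative-correlation argument falls away. But two places define the measurements as changes, so the text contradicts itself and must be reconciled either way.

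What the reply does not remove is that, on adjacent changes, the well-behaved booster and 8-week tests cannot show sustained benefit, and the contrast that could is the one with the wrong standard error.

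**Conclusion.** The point holds conditionally. If the modelled outcome is the adjacent change, as section 2.3 and the opening summary say, a random intercept is the wrong dependence structure. The averaged group effect then has a standard error up to 1.73 times too large. For the smallest planned effect at alpha 0.01, power is about 55% instead of 98% at 40 per arm and about 20% instead of 85% at 25 per arm with exchangeable scores. The loss shrinks as serial correlation rises, is smaller for pain, and vanishes for a random walk.

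The named tests keep roughly their nominal level, and the planned post-training power survives. The practical defect in them is interpretive: the booster and 8-week comparisons measure only the latest step. All sizes rest on assumed visit correlations, equal variances, balanced data, and an effect reached by post-training and then kept. This is a correction the plan should make, not a fault that invalidates its stated tests.

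**What to change.** In section 2.3, make the outcome the observed value at post-training, booster and 8 weeks. Use the baseline value as covariate; group, visit and group-by-visit as fixed effects; an unstructured within-patient covariance (REPEATED, TYPE=UN); and Kenward-Roger degrees of freedom. Test the group LS-mean difference at each visit. Each test then measures benefit since baseline. Amend the definition of the time index to match.

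If the adjacent changes are kept, replace the random intercept with TYPE=UN and test 8-week benefit as the sum of the three changes. In simulation, an unstructured test of group-by-time rejected 4.5-5.4% at nominal 5%.

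The cost is a short edit to the model description, one line of SAS code and a few more covariance parameters to estimate. No extra data are needed.

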1.2. Specific Aims

This study fulfills the national VHA/DoD Task Force recommendation that complementary, integrative therapies for pain management be provided to Veterans. Chronic pain elicits stress which increases sympathetic output fostering autonomic nervous system imbalance, an overextended stress response, fatigue, depression and insomnia. Heart Rate Variability (HRV) is a measure of the interplay between the sympathetic and parasympathetic nervous systems, and thus is a useful and easily-measured index of autonomic balance that has a relationship to chronic pain effects. HRV biofeedback (HRV-B) is a novel, biobehavioral procedure that restores normal autonomic balance. Through HRV-B, patients increase parasympathetic cardiac output and restore autonomic balance via induction of 'HRV coherence'. Our pilot study indicated that HRV-B produced coherence and alleviated self-reported ratings of chronic pain and stress among Veterans attending our Pain Clinic.⁵⁰ The proposed clinical intervention will further test hypotheses that HRV-B increases HRV coherence, reduces self-reported pain, stress, depression, fatigue, and insomnia, and improves cognition among Veterans with chronic pain.

The **specific aims** are to: (1) conduct a randomized, sham-controlled, pilot intervention trial to determine whether HRV-B increases HRV coherence among chronic pain patients (n=40 each for the HRV-B and sham treatment groups; total N=80 patients); (2) determine whether HRV-B reduces self-reported pain and stress among chronic pain patients. The primary endpoints include HRV coherence, pain (Brief Pain Inventory or BPI), and stress (Perceived Stress Scale or PSS).

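### With time as a nominal factor the plan makes 15 primary comparisons but divides 0.05 by 10, so its overall 0.05 is not guaranteed

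*Combined protocol and SAP*

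**What the plan says.** The Statistical Power & Sample Size paragraph of section 2.3 names five "primary study outcomes (HRV coherence, pain rating, negative emotion, activity limitation, perceived stress scale") and describes the error control: "An overall significance level of 0.05 was used with correction for multiple testing via the Bonferroni method for the 5 outcomes", giving 0.01 per outcome ("adjusted significance level = 0.01; 0.05/5").

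The Statistical Analyses part of the same section lets time be nominal or ordinal, the choice resting on model assumptions and BIC. If it is nominal, least-squares means are compared between groups "at each of the post-intervention time points (post-training, booster, 8-week follow-up"). For that case the plan sets its threshold: "In this situation we will use a Bonferroni adjusted alpha level = 0.005 (0.05/10), which results in at least 78% power", said to apply to every outcome with 25 per group. The calculation behind the 78% is not shown, and the divisor of 10 is not explained.

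Section 1.2 gives a shorter list: "The primary endpoints include HRV coherence, pain (Brief Pain Inventory or BPI), and stress (Perceived Stress Scale or PSS").

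**The concern.** A Bonferroni divisor should equal the number of tests in the family. The plan's own text gives five outcomes and three visits, and 10 is neither their product nor any other count that the plan states. Nothing in the documents reduces the count: there is no single primary visit, no gatekeeping order and no global test.

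If the nominal-time model is chosen, this threshold decides whether each primary outcome is declared significant. A threshold that does not bound the error at the plan's stated 0.05 weakens any positive claim resting on it. A p-value between 0.0033 and 0.005 would count as significant under the plan but would not meet a true Bonferroni correction for the five-outcome family.

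**Working it through.** **Inputs (section 2.3).** Overall alpha 0.05; five primary outcomes; three post-intervention visits; threshold 0.005; two-sided two-sample t-tests. The Table 3 differences in mean change and SDs are: negative emotion 15.5 − 4.5 = 11, SD 10; activity limitation 14 − 4 = 10, SD 9.5; pain rating 10 − 1.8 = 8.2, SD 5.0; perceived stress 4 − (−1.2) = 5.2, SD 4.5; HRV coherence 0.17 in absolute value, SD 0.15.

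**Step 1: reproduce the plan's power.** Power comes from the noncentral t distribution with 2n − 2 degrees of freedom and noncentrality (difference/SD) × √(n/2). At alpha 0.01 this matches Table 3; activity limitation, for example, gives 78.1%, 84.5%, 91.7% and 97.9% at 22, 25, 30 and 40 per group. At alpha 0.005 and 25 per group, activity limitation has noncentrality (10/9.5) × √12.5 = 3.72 and critical value 2.94 on 48 degrees of freedom. Its power is 77.7%, which rounds to the stated 78%. The power figure is therefore right for a threshold of 0.005.

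**Step 2: count the tests.** 5 × 3 = 15, so the Bonferroni level is 0.05/15 = 0.0033. A divisor of 10 would fit five outcomes at two visits, but the plan names three. The three-endpoint list gives 3 × 3 = 9 tests, for which 0.05/9 = 0.0056.

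**Step 3: which family does the sentence describe?** At 0.005 and 25 per group, power is:

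- activity limitation 77.7%
- negative emotion 82.2%
- HRV coherence 84.9%
- perceived stress 86.6%
- pain rating 99.7%

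Only activity limitation yields 78%. For pain rating, perceived stress and coherence alone, the minimum would have been 84.9%. The sentence was thus computed on the five-outcome family.

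**Step 4: error at 0.005.** The Bonferroni bound is 15 × 0.005 = 7.5%. With independent tests the error is 1 − 0.995^15 = 7.2%. The documents give no correlations, so equal correlations between outcomes and between visits were assumed and 15 null tests simulated (normal test statistics, 400,000 replicates):

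| Outcome correlation | Visit correlation | Family-wise error |
|---|---|---|
| 0 | 0 | 7.2% |
| 0.3 | 0.5 | 6.5% |
| 0.5 | 0.5 | 5.9% |
| 0.5 | 0.7 | 5.3% |
| 0.7 | 0.7 | 4.4% |
| 0.7 | 0.8 | 3.9% |

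A separate simulation with t-tests on 25 per group (40,000 replicates) gave 4.2% to 7.2% over the same range. At 0.0033 the error stayed at or below 4.9% throughout. For nine tests at 0.005 the bound is 9 × 0.005 = 4.5%.

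**Step 5: cost of the matching threshold.** Power at 25 per group:

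| Outcome | 0.005 | 0.0033 |
|---|---|---|
| Activity limitation | 77.7% | 73.2% |
| Negative emotion | 82.2% | 78.2% |
| HRV coherence | 84.9% | 81.3% |
| Perceived stress | 86.6% | 83.3% |
| Pain rating | 99.7% | 99.5% |

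At the planned 40 per group the minimum at 0.0033 is 95.0% (96.3% at 0.005).

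**The case against.** The best defence is that the primary family has three members. Section 1.2 says so. The section 2.0 overview, the questionnaire-outcomes paragraph of section 2.2 and the opening of Statistical Analyses also list coherence, pain and stress. On that reading there are nine tests, and 0.005 is slightly conservative. The reading does not fit the disputed sentence, however. Its 78% comes from activity limitation, and the power paragraph says expressly that the correction is for five outcomes. The three-endpoint list also does not say which BPI scale stands for pain.

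It can also be said that 0.005 is fixed numerically in advance, so the investigators cannot choose the threshold later. That is correct. What stays open is which outcomes count as primary, and hence whether the fixed threshold is adequate.

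Finally, the effect is conditional and modest. It arises only in the nominal-time branch. Independence of all 15 tests is implausible when visits are repeated on the same patients and, as in the pilot, four scale scores come from two instruments. The likely excess is therefore below the maximum, and the trial calls itself a pilot. This limits the size of the problem but does not supply the missing guarantee.

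**Conclusion.** The point holds. On the five-outcome family used for the plan's alpha and power, 0.05/10 does not match the 15 comparisons of the nominal-time analysis and bounds the family-wise error at 7.5%, not 5%. The realised excess is about 2 points at most and is absent when outcomes and visits are both strongly correlated; these figures rest on assumed equal correlations. The 78% is correct for 0.005, so only the divisor is wrong for the family. The conclusion would change only if the primary family were formally limited to three measures, which the documents do not do consistently. It should be fixed, and the consequence is moderate.

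**What to change.** Make the divisor match the family by one of these routes, and state which was chosen before the data are examined by group.

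1. Keep five outcomes and three visits: replace the threshold with 0.0033 (0.05/15) and restate minimum power at 25 per group as about 73% (activity limitation; the other four stay at or above 78%).
2. Adopt three primary endpoints: name one measure for each, make section 1.2 and the power paragraph of section 2.3 agree, and use 0.05/9 = 0.0056. With the Table 3 pain rating, perceived stress and coherence, minimum power at 25 per group is 85.8% (coherence).
3. Name one primary visit and keep five outcomes: the existing 0.01 then applies, with the Table 3 minimum of 84.5% at 25 per group. The other visits become secondary.

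Each route is a short text change. Route 1 costs 77.7 − 73.2 = 4.5 points of power for the weakest outcome at 25 per group. No route changes the sample size or the data collected.
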